# LIST OF ABBREVIATIONS

# 1 NASAL GUIDE

# **2 STUDY OBJECTIVES**

To determine the safety of the nasal guide during administration of Tyrvaya® (varenicline solution 0.03 mg) Nasal Spray.

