# **3** CLINICAL HYPOTHESIS

This study is testing the hypothesis that the use of the nasal guide with Tyrvaya® does not introduce any additional safety concerns as compared to the safety of Tyrvaya® alone.

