#### 8.9 Monitoring and Quality Assurance

9 SAFETY DEFINITIONS, MONITORING AND REPORTING

#### 9.1 Adverse Events

An adverse event (AE) is defined as any untoward medical occurrence associated with the use of a drug or device in humans, whether the event is considered drug or device related or not. An AE can therefore be any unfavorable and unintended sign (e.g., an abnormal laboratory finding), symptom, or disease occurring after the subject started dosing with the device, without any judgment about causality. Any pre-existing medical condition that worsens after administration of the nasal guide will also be considered a new AE.

AE collection will start following the first administration of Tyrvaya® utilizing the nasal guide until the last follow up visit of the study.

Documentation regarding the AE should be made as to the nature, date of onset, end date, severity, relationship to study drug, action(s) taken, seriousness, and outcome of any sign or symptom observed by the Investigator or reported by the subject upon indirect questioning.

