#### 9.1.2 Relationship

The relationship of each AE to the investigational product should be determined by the Investigator (in a blinded manner) using these explanations:

- *Definite:* When there are good reason and sufficient documentation to demonstrate a direct causal relationship between investigational product and AE
- *Probable:* When there are good reasons and sufficient documentation to assume a causal relationship in the sense of plausible, conceivable, likely but not necessarily highly probable

Tyrvaya® Clinical Trial Protocol: OPP-009

- *Possible:* When there is sufficient information to accept the possibility of a causal relationship in the sense of not impossible and not unlikely, although the connection is uncertain or doubtful, for example, due to missing data or insufficient evidence.
- *None:* When there is sufficient information to accept a lack of a causal relationship, in the sense of impossible and improbable.
- *Unclassified:* When the causal relationship is not assessable for whatever reason due to insufficient evidence, conflicting data, or poor documentation.

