8.10 Safety Analysis	
Appendix 1 Schedule of Visits and Measurements	

1 Synopsis

Protocol Title:	A Phase 4, Single-Center, Open-Label Study Evaluating the Safety of the Nasal Guide Utilized During Administration with Tyrvaya®
Protocol Number:	OPP-009
Investigational Product:	Nasal guide
Study Objective:	To determine the safety of the nasal guide when utilized to aid in the administration of Tyrvaya® (varenicline solution 0.03 mg) Nasal Spray
Treatment Assignment	30 subjects will be provided the nasal guide to utilize with Tyrvaya® administration.
Sample Size and Power	
Randomization and Stratification	Not applicable
Study Endpoints	Primary endpoints Incidence of adverse events
Statistical Analysis for Primary Endpoint	The AE data collected from this study will be summarized with frequency and percentage. The profile of the adverse events will be made by comparing the results from this study with the external historical AE data collected for Tyrvaya® alone from OC-01 (varenicline solution) nasal spray Integrated Summary of Safety (ISS). The data comparison will be made without inferential statistics.
Analysis Population	

Abbreviations

AE	adverse event
BID	two times a day
FDA	Food and Drug Administration
HIPAA	Health Information Portability and Accountability Act
ICH	International Conference on Harmonization
MedDRA	medical dictionary for regulatory activities
mg	Milligram
SAE	serious adverse event
SAE SAP	serious adverse event Statistical Analysis Plan
2112	
SAP	Statistical Analysis Plan
SAP SD	Statistical Analysis Plan Standard deviation

2 Introduction

This statistical analysis plan (SAP), which is based on the original protocol of the study protocol dated May 02, 2023, defines the methods, and analyses that Oyster Point Pharma, Inc. (henceforth, Oyster Point) plans to use to analyze and summize the data from Protocol OPP-009. This SAP complies with guidance promulgated by the International Conference on Harmonization (ICH) and the US Food and Drug Administration (FDA). If the protocol is subsequently amended, this SAP may be amended as well. Should the SAP and the protocol be inconsistent with respect to the planned analyses, the language of the SAP prevails.

3 Study objective

The objective of this study is to determine the safety of the nasal guide during administration of Tyrvaya® (varenicline solution 0.03 mg) Nasal Spray.

4 Study Design

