8.10 Safety Analysis

8.10.1 Adverse Event

The investigator will promptly review each Adverse Event (AE) for accuracy and

completeness, and classify each AE according to its intensity, its re

administration procedure, and its seriousness. AEs will be coded using version 26.0 of the MedDRA dictionary. AEs will be monitored throughout the study and documented on the appropriate AE form. AEs will be categorized as ocular and non-ocular events as well as by system organ class (SOC) and preferred term (PT), seriousness, severity, and relation to study medications.

All treatment-emergent adverse events (TEAEs) will be summarized. A TEAE is defined as an AE that is new or worsened in severity compared to the first dose of study drug.

TEAEs will be summarized by subject. In addition, the number of TEAE episodes that occurred during the study will be provided in the overall summary of AE table. All AEs will be presented in data listing with a flag indicating the event is a TEAE.

The following presentations of TEAEs will be generated:

- Overall adverse events summary (including any TEAEs, ocular TEAEs, resolved ocular TEAEs, non-ocular TEAEs, SAEs, treatment emergent SAEs, treatment-related treatment emergent SAEs, TEAEs by maximum severity, TEAEs by relationship to study drug, AEs leading to treatment/study discontinuation)
- All TEAEs by SOC and PT
- All ocular TEAEs by SOC and PT
- All non-ocular TEAEs by SOC and PT
- Resolved ocular TEAEs by SOC and PT
- Serious adverse events (SAE) by SOC and PT
- Serious treatment-emergent adverse events (TESAE) by SOC and PT
- Related treatment-emergent serious adverse events (TESAE) by SOC and PT
- TEAEs by SOC and PT and by severity
- TEAEs by SOC and PT and by relationship
- TEAEs by SOC and PT leading to treatment discontinuation
- TEAEs by SOC and PT leading to study discontinuation

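### Nasal guide safety is the only objective, yet the visible AE causality wording mostly targets the drug and none of the planned causality tables names the guide

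*SAP*

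**What the plan says.** The objective in protocol section 2 is "To determine the safety of the nasal guide during administration of Tyrvaya", and the SAP synopsis repeats it: "To determine the safety of the nasal guide when utilized to aid in the administration of Tyrvaya". The hypothesis in protocol section 3 is that using the guide "does not introduce any additional safety concerns as compared to the safety of Tyrvaya" alone.

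The AE definition in protocol 9.1 recognises that either product may be a cause, since an event counts "whether the event is considered drug or device related or not". The documentation list in the same section then names one object only: "date of onset, end date, severity, relationship to study drug, action(s) taken, seriousness, and outcome". Protocol 9.1.2, which holds the five-category scale, names another: "The relationship of each AE to the investigational product should be determined by the Investigator (in a blinded manner"). The bracketed mention of blinding has no application in an open-label, single-arm study and plays no part in this point.

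On reporting, SAP 8.10.1 first says that AEs are categorised by their relation to the study medications. It then lists the presentations, among them an overall summary that includes "TEAEs by maximum severity, TEAEs by relationship to study drug, AEs leading to treatment/study discontinuation".

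**The concern.** When a study exists to assess an accessory, the natural causality question is whether the accessory contributed to the event. The visible text never sets up that question as a rating separate from the drug. A nasal event that the investigator attributes to the guide and not to varenicline has no clear place in the record. Under some sections it would be entered as unrelated. Under others it would be entered as related but pooled with drug effects.

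What is at stake is how the causality tables read. A reader of the report who looks for guide-related events would find rows about the drug and could take a low count as reassurance about the guide.

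**Working it through.** The plan gives no figure to reproduce here. The check is a count of presentations and a comparison of wording.

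**Step 1. Count the AE presentations.**
- SAP 8.10.1 lists 12. Three use causality: the overall summary, the related treatment-emergent SAEs by SOC and PT, and the TEAEs by SOC and PT and relationship. None of the 12 names the guide, the device or the administration procedure.
- Those 3 hold 4 causality entries. The overall summary has two: treatment-related treatment-emergent SAEs, and TEAEs by relationship to the drug. The other two are stand-alone tables whose titles name no object.
- Protocol 10.3.2 lists 6. One uses causality (the overall summary), and none names the guide.

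**Step 2. Set the causality objects side by side**, and ask how each would class an event that the investigator attributes to the guide alone.

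| Place | Object of causality | Guide-only event would be |
|---|---|---|
| Protocol 9.1, documentation | study drug | unrelated |
| Protocol 9.1.2, rating scale | investigational product | related if this means the guide, as in the SAP synopsis; unrelated if it means the drug |
| Protocol 9.3.2, SAE case history | study drug | unrelated |
| Protocol 10.3.2, classification by the investigator | drug or administration procedure | arguably related, but not necessarily distinguished from a drug effect |
| Protocol synopsis, study treatment | Tyrvaya given with the guide | related to the combination |
| SAP 8.10.1, categorisation | study medications | unrelated |
| SAP 8.10.1, overall summary row | study drug | unrelated |

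**Step 3. Ask whether the precedence rule settles it.** SAP section 2 states: "Should the SAP and the protocol be inconsistent with respect to the planned analyses, the language of the SAP prevails". Applied to the tables, this leads to the SAP wording, which means the drug. It therefore favours the reading that leaves the guide out. The rule also covers planned analyses; it does not tell the site what to rate on the AE form.

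**Step 4. Ask what depends on causality.** The primary endpoint is the incidence of all AEs (SAP 5.1). The comparison with the Tyrvaya-alone Integrated Summary of Safety is descriptive (protocol 10.3, SAP synopsis) and is not described as depending on relatedness. All AEs go to the sponsor (protocol 9.3), and SAEs are reported within 24 hours whatever their relationship to the device (protocol 9.3.2). Only the causality entries counted in step 1 are affected.

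**The case against.** The strongest reply is that causality is not how this study answers its question. The hypothesis is comparative, the planned answer is a descriptive comparison with historical data, and every planned dose is given with the guide. Separating drug from guide is then unblinded opinion with no counterpart in the drug-alone data. This stands, and it limits the weight of the point. It does not remove it: the sponsor has chosen to produce causality tables, and in a guide study they should at least be able to show the guide.

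A second reply is that the deciding text may be out of sight. The eCRF is not shown, and the SAP sentence on classification is cut off in the available text just where the object would stand; the fragment that survives mentions the administration procedure. This also stands. A guide field may exist. It would not by itself put the guide into the listed tables or reconcile the protocol sections.

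Some stronger readings are tempting and are not supported:

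- *A reader might infer that the SAP contradicts itself*, because its synopsis names the guide as investigational product while 8.10.1 tabulates by drug. But 8.10.1 does not use the term investigational product, and different terms for different things are not a contradiction.
- *A reader might infer that the two untitled-object tables are really guide tables.* The lead-in on study medications naturally supplies their object, so the plainer reading is that they concern the drug.
- *A reader might add the expectedness categories in protocol 9.1.3*, where an event unrelated to the drug and not listed could fit two categories. That would arise for any unrelated, unlisted event, so it is not specific to the guide, and no listed SAP presentation uses expectedness.
- *A reader might size the effect as 1/30 = 3.3 percentage points per subject.* That is the step for any one subject in any table of 30. The documents give no rate of guide-only events and no cut that turns the five categories into related and unrelated.

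**Conclusion.** The point holds as a cheap improvement. The sole objective concerns the guide, the visible causality wording mostly concerns the drug, and the remaining sections use objects that differ from it and from each other. Its size is the count: 3 of 12 SAP presentations use causality and 0 name the guide; in the protocol, 1 of 6 and 0. The consequence is that an event caused only by the guide could be tabulated as unrelated.

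It would be wrong to infer that the primary result is compromised. The all-AE incidence, the descriptive historical comparison and SAE reporting do not change. The conclusion assumes that the AE form follows the visible protocol wording and that the truncated SAP sentence adds no separate guide rating. If a separate guide field already exists, what remains is to align the terms and name the guide in the tables.

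**What to change.** 1. Use one set of terms for the drug, the guide and their combined use in protocol 9.1, 9.1.2, 9.3.2 and 10.3.2 and in SAP 8.10.1.
2. Record two fields on the AE form: relationship to Tyrvaya, and relationship to the nasal guide (or to administration with it).
3. In SAP 8.10.1, name the object in each causality row and title.
4. Add a table of TEAEs by SOC and PT by relationship to the guide, and state that it is an unblinded supplement to the historical comparison.

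The cost is one more eCRF field, wording changes in both documents, a few added or relabelled tables and one more unblinded judgement per AE. No visits, procedures or subjects are added. The extra field needs to be in place when events are rated, because relabelling tables cannot supply a rating that was never asked for.

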8.10.2 Concomitant Medications

Concomitant medications will be coded using the World Health Organization Drug Dictionary (March 2023 version) and summarized in the safety population. Any medication taken from the day of first dose of the study treatment up to the day of last date of the study will be considered as a concomitant medication for analysis.

Appendix 1 Schedule of Visits and Measurements
